10.0 Data and Specimen Banking: Not Applicable

10.1. *Data analysis*

Specific Aim 1 (Feasibility; Primary Aim): To demonstrate the feasibility of the PATH intervention in patients with hematologic malignancy undergoing HSCT: Based on prior work, we define feasibility as >75% of enrolled participants who start the intervention completing at least 6 of the

PROTOCOL TITLE: Randomized Trial of a Positive Psychology Intervention for Patients with Hematologic Malignancies Undergoing Hematopoietic Stem Cell Transplantation

9 PP sessions, consistent with metrics used in prior positive psychology feasibility trials^{17, 54} and other behavioral intervention studies.⁸⁵⁻⁸⁷ We will estimate the feasibility using the proportion who meet the criteria, and we will place an exact 95% binomial confidence interval around the proportion. We will assess acceptability using weekly ratings of ease and utility of each exercise (0=very difficult/not helpful; 10=very easy/very helpful). The mean ease and utility of each exercise and overall will be calculated, and will use a threshold of a mean combined score of 7.0/10 for acceptability that was used in prior studies.^{19,57}

Specific Aim 2 (Effects on Patient-Reported Outcomes): To assess the preliminary efficacy of the PATH intervention on psychological (e.g., depression, anxiety, optimism, positive affect), QOL, and functional outcomes compared to the usual care condition: Analyses will begin with descriptive and graphical summaries of the endpoints and evaluation of whether a normality assumption is reasonable for the endpoint or whether transformation is necessary. We will use a Bonferroni correction to address multiple measures and testing. All statistical tests will be two-sided with a liberal alpha level of 0.2 to detect a signal on the impact of the intervention on patient- reported outcomes. We will summarize participants' baseline characteristics using descriptive statistics (e.g., mean) for continuous variables and proportions for categorical variables.

To examine the immediate impact of the intervention on happiness and optimism, we will use generalized estimating equations (GEE) to determine the immediate impact of a PP session on optimism and happiness. The GEE model will allow us to account for the repeated observations on subjects from the different exercises.

We will compare between-group differences in change over time in all patient-reported outcome measures (i.e., psychological, functional, and QOL outcomes) at the 9 and 18-week time points using random effects regression models with a random intercept for each patient. Longitudinal analyses will include all time points. The model will include a categorical effect of time (baseline, week 9 and week 18), a group effect and a time by group interaction. The time by group interaction will estimate the difference in the change from baseline to each time point, and these regression coefficients will be the focus of the analysis.

Given that this pilot is not powered to detect statistically significant group differences, we will examine difference in the change with time and sample variance components on the secondary outcomes. Effect sizes (Cohen's d) will be calculated for changes in outcomes from baseline to 9 and 18 weeks, where 0.3 indicates a small effect, 0.5 a medium effect, and 0.8 a large effect.⁸⁸ Effect sizes will be used in a power analysis to estimate the necessary sample size to conduct a full-scale efficacy trial with power >80%. We will also verify the needed sample size based on ability to detect a clinically meaningful difference and references to existing literature.⁸⁹

Finally, we will explore (1) possible mediators of the intervention (e.g., coping strategies) by examining the bootstrapped confidence intervals of the indirect effects and (2) possible moderators (e.g., social support) of intervention effects by probing interactions between the moderator and group assignment that reach or approach significance ($p<0.15$) when predicting patient-reported outcomes.

PROTOCOL TITLE: Randomized Trial of a Positive Psychology Intervention for Patients with Hematologic Malignancies Undergoing Hematopoietic Stem Cell Transplantation

Specific Aim 3 (Effects on Health Behaviors): To examine the impact of the PATH intervention on behavioral outcomes (e.g., medication adherence, physical activity) compared to those in the usual care condition: We will initially compare physical activity (# of steps/day) at 9- and 18-weeks between the intervention and control groups using a Wilcoxon rank sum test, given that the distribution of the number of steps will likely be skewed. We will also use random effects regression models with a random intercept for each participant to compare between-group differences in change over time in physical activity and medication adherence. All statistical tests will be two tailed, with $p < 0.05$ considered significant.

Missing Data: We will also use the intention-to-treat principle with all randomized participants and conducting sensitivity analyses to explore various assumptions about missing data. If source of the missing data appear to be missing at random, the linear mixed effects models described above provide an unbiased estimate of the regression coefficients. However, if we find that participants do not complete the study because of disease worsening, suggesting missing data are not random, we will employ pattern mixture modeling or joint modeling approaches⁹⁰ to handle incomplete data, and perform sensitivity analysis⁹¹ to assess the impact of missing data. In addition to the intention-to-treat analysis, we will also estimate the group differences in the completers to estimate the per protocol group difference.

10.2. Sample Size Calculation & Power Analysis:

Based on prior trials in this population,⁹² we anticipate 15% of enrolled participants will be unable to complete the intervention due to medical complications and mortality. Hence, we will enroll 70 participants (35 in the [PATH] PP arm) to target having at least 30 PP participants who complete the intervention. For our primary aim (feasibility), in prior trials, approximately 80% of participants have completed 6 of 9 PP exercises.⁹ Using the same rate, with 30 PATH participants, we will have 95% power (two-sided $\alpha = .05$, binomial proportion test) to demonstrate that the proportion who complete > 6 of 9 PP sessions is larger than 50% (i.e., a majority). For acceptability, using this sample size, we will have 95% power to detect a true mean score of > 7.0 based on prior work (in which mean utility scores were 7.8 ± 1.8).¹² This pilot RCT is not designed to definitively detect significant ($p < .05$) group differences in psychological, QOL, or behavioral outcomes (and we would need between-group effect size differences of $d = .74$ to be powered at 80% to detect significant differences). However, this sample of 30 completers in each group will allow us to preliminarily explore the impact of PATH on clinical outcomes and make tentative estimations of effect sizes.

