1.2 Specific Aims/Objectives

#1 (Feasibility; Primary Aim): To determine the feasibility and acceptability of the PATH intervention in patients with hematologic malignancy undergoing HSCT.

PROTOCOL TITLE: Randomized Trial of a Positive Psychology Intervention for Patients with Hematologic Malignancies Undergoing Hematopoietic Stem Cell Transplantation

Hypothesis: The PATH intervention will be deemed feasible with >75% of participants randomized to the intervention arm completing ≥ 6/9 positive psychology exercises. The PATH intervention will be deemed acceptable with mean ease and utility scores of each exercise being ≥ 7/10.

#2 (Effects on Patient-Reported Outcomes): To assess the preliminary efficacy of the PATH intervention on psychological (e.g., depression, anxiety, optimism, positive affect), QOL, and functional outcomes compared to the usual care condition.

Hypothesis: Patients randomized to the PATH intervention will have improved PPWB (e.g., optimism, positive affect, gratitude), mood (e.g., depression and anxiety), and QOL compared to those in the usual care condition.

#3 (Effects on Health Behaviors): To examine the impact of the PATH intervention on behavioral outcomes (e.g., medication adherence, physical activity) compared to those in the usual care condition.

Hypothesis: Patients randomized to the PATH intervention will have improved behavioral outcomes (e.g., medication adherence, physical activity) compared to those in the usual care condition.

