Participants will be registered with the Clinical Trials Management System after they have consented, provided baseline *Actigraph GT3X+* data, and completed baseline assessments. If participants provide consent but do not complete baseline Actigraph data collection and assessments, they will not count towards accrual numbers. Participants who withdraw from the study or die during the study period will not be replaced and they will count towards accrual numbers.

DF/HCC institutions will register eligible participants in the Clinical Trials Management System (CTMS) Oncore as required by DF/HCC SOP REGIST-101. Registration must occur after the initiation of protocol-specific procedures or assessments.

For registration of participants from the DF/HCC institutions, study staff will complete the DF/HCC protocol-specific eligibility checklist. Study staff will confirm that the participant meets all inclusion criteria as described in this protocol. Study staff will then register study participants through OnCore. Study staff will follow DF/HCC Standard Operating Procedure for Human Subject Research Titled *Subject Protocol Registration* (SOP #: REGIST-101) and register the participant on the protocol.

Once the patient has been registered, a member from the MGH Cardiac Psychiatry Research Program (CPRP) team or the Cancer Outcomes Research and Education Program (CoRE) (independent from the study staff) will perform randomization procedures using a computer-generated randomization schema, stratified by GVHD status.

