9.7 Overview of Research Procedures

Initial/Enrollment phone call: During this initial approach at a routine outpatient follow-up clinic or phone call, the study procedures will be explained to potential participants. Those who are interested will be screened for eligibility and, mailed or e-mailed a copy of the study information

PROTOCOL TITLE: Randomized Trial of a Positive Psychology Intervention for Patients with Hematologic Malignancies Undergoing Hematopoietic Stem Cell Transplantation

sheet. We will then call patients upon receipt of the information sheet approximately seven days from receipt of the information sheet for enrollment and written consent procedures during a routine clinic visit or verbal consent procedures over the phone. Consented participants will then be randomized to usual care or the intervention group. All participants will be mailed (or given in person at a routine follow-up visit) the electronic pill bottle (MEMS Caps), and the accelerometer (Actigraph GT3X+, small half-dollar sized device that clip on to a belt with no visible readout thus preventing independent subject access to data) to wear for 7 days prior to the intervention initiation in the control group. Participants in the intervention group will also be mailed the study intervention manual together with their accelerometer and electronic pill bottle. At the time of the baseline survey and prior to the start of the intervention, adequate accelerometer wear (at least 4 days with 10+ hours per day worn) will be confirmed. Participants in the intervention group will also be mailed the study intervention manual. Those who have not completed sufficient wear of the device will be asked to re-wear the device until there is sufficient baseline data available.

Baseline Assessments: Around the time of each participant's routine 85-95-day post-transplant routine clinic visit, participants will be asked to complete baseline assessment questionnaires either in person during a routine follow-up visit in clinic, over phone, or via a REDCap survey link that will be e-mailed to participants.

After completion of the baseline survey and a returned accelerometer with adequate data, the interventionist will review the mailed treatment manual with weekly PP exercises to those in the intervention group. Participants in the intervention group will be assigned the first exercise (gratitude for positive events) in preparation for their first phone session.

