- **Disease Worsening/Mortality:** Given the burden of treatment for patients with hematologic malignancies undergoing HSCT, we do anticipate that a minority of participants will be unable to complete the study protocol due to deteriorating health or death. Our research team has given considerable thought to this concern and adequately powered the study to account for missing data. Based on prior work, we anticipate a 15% attrition rate. The study CRCs will maintain detailed records for patient attrition due to disease-related factors.
- **Refusal to Participate:** Participants who are successfully recruited into the study but later refuse to participate in subsequent intervention sessions pose a threat to the proposed study. In our previous trial, our refusal to participate rate after study enrollment was quite low and all participants who started the intervention actually completed the all the intervention sessions. Again, the CRCs will maintain detailed records for patient refusals.
- **Loss of Contact:** Another source of attrition involves those subjects who are successfully recruited into the study but who cannot be located for subsequent follow-up assessments. Like attrition due to subject refusal, attrition due to loss of contact poses a threat to the proposed study. We do not anticipate this to be a major

PROTOCOL TITLE: Randomized Trial of a Positive Psychology Intervention for Patients with Hematologic Malignancies Undergoing Hematopoietic Stem Cell Transplantation

issue for the proposed study given the intensive and frequent outpatient follow-up visits for patients with hematologic malignancies during the first six months post-HSCT.

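### The primary >75% feasibility criterion is stated on two denominators, everyone randomised to PATH and only those who start it, and nothing reconciles them

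*Combined protocol and SAP*

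**What the plan says.** - **Section 1.2, Aim 1** sets the feasibility hypothesis as ">75% of participants randomized to the intervention arm completing ≥ 6/9 positive psychology exercises".
- **Section 10.1, Specific Aim 1** sets it differently: "we define feasibility as >75% of enrolled participants who start the intervention completing at least 6 of the" nine sessions. The proportion is to be reported with an exact 95% binomial interval.
- **Section 8.0** names feasibility as part of the primary endpoint without giving a denominator.
- **Section 9.7** places randomisation straight after consent: "Consented participants will then be randomized to usual care or the intervention group". Devices are then issued, and the interventionist begins only after the baseline survey and adequate accelerometer data.
- **Section 5.1** registers participants after consent, baseline accelerometer data and baseline assessments, and only then randomises: "Once the patient has been registered, a member from the MGH Cardiac Psychiatry Research Program (CPRP) team" or another independent group does so. Section 21.0 likewise registers after the baseline questionnaires and randomises after registration.
- **Section 10.2** says "we anticipate 15% of enrolled participants will be unable to complete the intervention due to medical complications and mortality", enrols 35 per arm "to target having at least 30 PP participants who complete the intervention", and claims 95% power with 30 PATH participants "to demonstrate that the proportion who complete > 6 of 9 PP sessions is larger than 50" per cent, taking a true rate of 80%.

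**The concern.** Feasibility is the primary aim, so its pass rule should have one denominator, fixed in advance. Here there are two in current text. No sentence says which governs, what counts as starting, or how a participant randomised to PATH who never starts is to be counted. The intention-to-treat sentence in Section 10.1 sits under Missing Data beside the mixed models. If it did extend to the feasibility rate, it would contradict the starters wording rather than resolve it.

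The starters rule can never be the stricter one. A non-starter adds nothing to the numerator and is dropped from the denominator. Any conflict therefore runs one way: feasible among starters, not feasible among all randomised. Session counts accrue in view of the study team, so an unfixed denominator leaves room for the choice to be made once the result is known.

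**Working it through.** **The plan's own figure.** Inputs from Section 10.2: n = 30, null 50%, true rate 80%, two-sided 5% level.

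- Normal approximation: Φ[(√30 × 0.30 − 1.96 × 0.50) / 0.40] = Φ(1.66) = 95.1%.
- Exact binomial: the rejection region starts at 21 of 30 (two-sided p = 0.043), and power at 80% is 93.9%.
- Attrition: 35 × 0.85 = 29.75, about 30.

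The stated 95% is reproduced. It concerns exceeding 50%, not the 75% criterion.

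**Where the two rules part.** Inputs: 35 randomised to PATH (Section 7.0, Table 1) and j non-starters. The documents do not give j, so j = 0 to 3 is assumed. Starters are m = 35 − j, and X is the number reaching six sessions.

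- Randomised rule: X/35 > 0.75 needs X > 26.25, so X ≥ 27.
- Starters rule: X must be at least k, the smallest whole number above 0.75m.
- The verdicts conflict when k ≤ X ≤ 26.

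With each starter reaching six sessions independently with probability p, X is binomial(m, p). The chance of conflict is the sum of P(X = x) for x from k to 26:

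| Non-starters (assumed) | m | 0.75m | k | Conflicting counts | p = 80% | 85% | 90% | 95% |
|---|---|---|---|---|---|---|---|---|
| 0 | 35 | 26.25 | 27 | none | 0 | 0 | 0 | 0 |
| 1 | 34 | 25.5 | 26 | 26 | 14% | 7% | 1% | <0.1% |
| 2 | 33 | 24.75 | 25 | 25, 26 | 30% | 17% | 4% | 0.1% |
| 3 | 32 | 24 | 25 | 25, 26 | 34% | 25% | 8% | 0.4% |

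Example: 26/34 = 76.5% (exact 95% CI 58.8% to 89.3%) passes, and 26/35 = 74.3% (56.7% to 87.5%) fails. The evidence is nearly identical and the verdicts are opposite.

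**Chance of meeting the >75% criterion with 35 as denominator.** P(X ≥ 27 | 35, p) is 74.5%, 93.1% and 99.4% at true all-randomised rates of 80%, 85% and 90%. At the threshold, 27/35 = 77.1% (exact 95% CI 59.9% to 89.6%).

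**Does the choice of denominator itself lower that chance?** At a true rate of 80% in whichever set is used, the chance of exceeding 75% is 77.3% with 34, 76.1% with 30 and 74.5% with 35. The size of the denominator alone changes little.

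**The case against.** The strongest reply is that the two sets may coincide. Sections 5.1 and 21.0 both place randomisation after baseline and registration. That leaves a short gap between baseline (about day 85–95) and the first call (about day 100), so few or no participants may be lost in it. Section 9.7 also reports 100% completion in the one-arm proof-of-concept study. At such rates a conflict is very unlikely even with three non-starters, and the trial is a pilot that reports an estimate with an interval. All of this stands, and it limits the size of the problem. It does not say which rule applies, and Section 9.7 still describes randomisation before baseline.

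A second reply is that Section 10.1 governs because it is the analysis section and cites metrics from prior feasibility trials. No text gives it precedence over Section 1.2.

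Three stronger readings are tempting, but the documents do not support them.

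- A reader might take the 30 in Section 10.2 as a third endpoint denominator. It is ordinary attrition planning and does not define the endpoint.
- A reader might infer from Section 11.0, where "all participants who started the intervention actually completed the all the intervention sessions", that losses fall before start and a starters-only rate would hide them. That earlier study had one arm and so no randomised non-starters. Its pre-start losses may have been people who would not be registered or counted towards accrual here.
- A reader might see a fall from 95% to about 75% as the price of using everyone randomised. The first figure is power against 50% and the second is the chance of exceeding 75%. They answer different questions.

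**Conclusion.** The concern holds. The primary criterion has two live denominators, and the text does not choose between them. The practical risk depends on two unknowns: the number of randomised non-starters and the rate among starters. Over 1 to 3 assumed non-starters, the chance of opposite verdicts is 14% to 34% at a rate of 80%, 7% to 25% at 85%, 1% to 8% at 90%, and under 0.5% at 95%. With no non-starters it is nil. These figures assume 35 randomised to PATH and independent participants with a common success probability.

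The 95% power statement is correct for what it claims and is not part of the error, but it says nothing about the >75% criterion. The strict inequality on six sessions in Section 10.2 is a clerical slip: Sections 1.2, 9.7 and 10.1 all say at least six. The denominator should be settled before the primary result is known, because afterwards the choice could decide the verdict.

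**What to change.** 1. In Sections 1.2 and 10.1, make all participants randomised to PATH the primary denominator, as Section 1.2 already has it. Count non-starters and those who stop before six sessions as not meeting the criterion.
2. Report the starters-only rate as secondary and define start, for example as the first phone session held.
3. Reconcile Section 9.7 with Sections 5.1 and 21.0 on when randomisation occurs, so that the randomised set is fixed.
4. State success as an observed proportion above 75%, at least 27 if 35 are randomised, and say that the exact 95% interval is descriptive.
5. Keep the 95% power statement in Section 10.2 if wanted, but say that it does not describe the >75% criterion. Add the chance of reaching 27 of 35: about 75%, 93% and 99% at true all-randomised rates of 80%, 85% and 90%.
6. Correct '> 6' to '≥ 6' in Section 10.2.

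The cost is wording, with no extra participants or data. The downside is that deaths and drop-outs before six sessions count against feasibility. Comparison with any prior trial that used a starters-only rate will rest on the secondary figure.

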3.0 Inclusion and Exclusion Criteria*

We propose a single center randomized controlled trial of the PATH intervention versus usual care in 70 patients (age ≥ 18) with hematologic malignancies who have undergone HSCT. Participants will be recruited from the Dana Farber Cancer Institute (DFCI) HSCT Program. Participants will be randomized equally to the two arms using randomized permuted blocks of sizes two and four, with randomization stratified by presence/absence of graft versus host disease (GVHD). As allogeneic transplant recipients with GVHD have significantly different courses of recovery, QOL, and function post-transplant, we will stratify by GVHD status to ensure adequate and balanced representation between the two study groups.

3.1 Screening Procedures:

Eligible study participants will be identified using the DFCI HSCT clinic database. The clinical research coordinator (CRC) will review the database to screen for eligible patients. We have utilized this study procedure in our proof-of-concept trial (18-225) and enrolled 56% of potentially eligible participants.

Patients who have been approved for the study by their HSCT oncologist will be contacted twice via telephone or in person at a routine clinic visit by a member of the study team after inclusion/exclusion criteria is assessed. Eligible patients will be screened and provided (in-person at clinic, mailed or e-mailed) an information sheet (Appendix A) of the study to review prior to their completing consent procedures.

PROTOCOL TITLE: Randomized Trial of a Positive Psychology Intervention for Patients with Hematologic Malignancies Undergoing Hematopoietic Stem Cell Transplantation

The DFCI will register eligible participants in the Clinical Trials Management System (CTMS) OnCore as required by DF/HCC SOP REGIST-101. When required by REGIST-101, registration must occur prior to the initiation of protocol-specific procedures or assessments.

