9.0 Procedures Involved*

9.1 Study Design

We propose a single center randomized trial of a positive psychology intervention (PATH) versus usual care in 70 patients with hematologic malignancies undergoing HSCT. Participants will be randomized equally to the two arms using randomized permuted blocks of sizes two and four, with randomization stratified by presence/absence of GVHD. As allogeneic transplant recipients with GVHD have significantly different courses of recovery, QOL, and function post-transplant, we will stratify by GVHD status to ensure adequate and balanced representation between the two study groups.

PROTOCOL TITLE: Randomized Trial of a Positive Psychology Intervention for Patients with Hematologic Malignancies Undergoing Hematopoietic Stem Cell Transplantation

The goals of this study are to assess the feasibility, acceptability and preliminary efficacy of this novel 9-session, weekly PP-based intervention for HSCT patients.

Patients will be contacted via telephone or in person at a routine clinic visit close to their routine 70-80-day post-transplant visit for eligibility determination. Interested patients will be screened based on the inclusion/exclusion criteria and provided a study information sheet via mail, e-mail or in-person at a routine clinic visit. Consent procedures would be completed in-person at a routine clinic visit or verbally over the phone approximately seven days after study information is provided.

Upon consent to participate in the study, participants will be given an electronic pill bottle (MEMS Cap) [to be used from the time of baseline assessment completion through the entire duration of the intervention], and an accelerometer to be worn for 7 days prior to the initiation of the intervention. Between the 85-95-day point, all participants will also complete baseline questionnaires either in person, over phone or via a REDCap survey link to participants. Additionally, participants randomized to the intervention group will be given an intervention manual with 9 weekly PP exercises.

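### The Aim 2 mixed model gives each arm its own baseline mean, so its effect estimates are unbiased but less precise than the collected data allow

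*Combined protocol and SAP*

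**What the plan says.** Section 10.1 (Specific Aim 2) compares all patient-reported outcomes with a random-intercept regression in which baseline is one of three outcome times: "The model will include a categorical effect of time (baseline, week 9 and week 18), a group effect and a time by group interaction". It continues: "The time by group interaction will estimate the difference in the change from baseline to each time point", and names these coefficients as the focus. Cohen's d is to be calculated for changes from baseline to weeks 9 and 18, and "Effect sizes will be used in a power analysis to estimate the necessary sample size to conduct a full-scale efficacy trial". The same section also checks the next sample size against a clinically meaningful difference and the literature. No section adjusts for the baseline score or sets the two baseline means equal.

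On who is analysed, Section 10.1 (Missing Data) says "We will also use the intention-to-treat principle with all randomized participants". Section 5.1 says "If participants provide consent but do not complete baseline Actigraph data collection and assessments, they will not count towards accrual numbers", so every participant who counts has a baseline score. Section 10.2 says "this sample of 30 completers in each group will allow us to preliminarily explore the impact of PATH on clinical outcomes".

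Randomisation is stratified by GVHD (Sections 3.0, 5.1 and 9.1) on the ground that "allogeneic transplant recipients with GVHD have significantly different courses of recovery, QOL, and function post-transplant". GVHD has no term in the Aim 2 model. Section 9.3 says that social-work consultation data will be considered as covariates, but Section 10.1 gives them no role.

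**The concern.** In a randomised trial the arms have the same expected baseline mean. A free group effect ignores this. Any chance baseline difference Δ between arms is then subtracted in full from the follow-up difference, although only a fraction ρ of it (the within-patient correlation) is expected to persist. The contrast is off by (1−ρ)Δ in that particular trial. This averages to zero over randomisations, so it is noise rather than bias.

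Aim 2 exists to estimate effect sizes for planning a larger trial, so precision is its main product. The information needed to recover it, baseline scores on the same instruments (Table 4), is already collected.

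**Working it through.** **The plan's own figure.** Section 10.2 gives d = 0.74 as detectable with 80% power. A two-sample t-test with 30 per arm and two-sided alpha 0.05 gives 0.736, and power of 80.5% at 0.74. The figure reproduces and is not in dispute. It is a two-group calculation that involves no ρ, and the plan does not say whether its SD is of raw scores or of changes.

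**Inputs.** 35 per arm with baseline (Sections 5.1 and 10.2); 30 per arm at weeks 9 and 18 (Section 10.2); outcome SD set to 1; equal correlation ρ between visits, as a random intercept implies. The documents do not give ρ, so a range of 0.3 to 0.9 is assumed.

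**Variance of the week-9 contrast** (week 18 is identical).

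- Planned model, free baseline means: V1 = 2[(1−ρ²)/30 + (1−ρ)²/35]
- Common baseline mean: V2 = 2(1−ρ²)/30
- Ratio: V1/V2 = 1 + (30/35)(1−ρ)/(1+ρ)

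At ρ = 0.5: V1 = 2(0.0250 + 0.00714) = 0.0643, V2 = 0.0500, ratio 1.286, and the SE ratio is √1.286 = 1.134.

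| ρ (assumed) | SE planned | SE common baseline | SE excess | Equivalent sample lost (1 − V2/V1) | 95% half-width, SD units |
|---|---|---|---|---|---|
| 0.3 | 0.298 | 0.246 | 20.9% | 31.6% | 0.58 vs 0.48 |
| 0.5 | 0.254 | 0.224 | 13.4% | 22.2% | 0.50 vs 0.44 |
| 0.7 | 0.198 | 0.184 | 7.3% | 13.1% | 0.39 vs 0.36 |
| 0.8 | 0.162 | 0.155 | 4.7% | 8.7% | 0.32 vs 0.30 |
| 0.9 | 0.115 | 0.113 | 2.2% | 4.3% | 0.23 vs 0.22 |

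**Bias check.** 4,000 simulated trials per ρ, with a true effect of 0.50 SD and about 15% dropout depending on baseline, gave means of 0.497, 0.511 and 0.496 for the planned model and 0.493, 0.507 and 0.497 for the common-baseline model at ρ = 0.3, 0.5 and 0.7. Neither shows material bias. The simulated variance ratios V2/V1 were 0.69, 0.77 and 0.88; the formula gives 0.68, 0.78 and 0.87.

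**Unequal correlations.** With complete data on 30 per arm and correlations of 0.6 (baseline to week 9), 0.4 (baseline to week 18) and 0.6 (week 9 to 18), the common-baseline model cuts the variance from 0.0533 to 0.0430 at week 9 and from 0.0800 to 0.0572 at week 18. The gain does not depend on equal correlation.

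**GVHD.** Assumed: 40% prevalence, a shift of 0.5 to 0.8 SD, ρ = 0.5; 1,000 simulated trials per case. Leaving out GVHD and GVHD-by-time raises the planned model's reported SE by about 0% if GVHD shifts all visits equally, and by 2–5% if it shifts follow-up only. In the common-baseline model the figures are 1–2% and 2–5%. The actual spread of the estimates changed by at most about 1.3% (0.239 vs 0.236).

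**Order of baseline and randomisation.** Section 5.1 registers participants after baseline and randomises after registration, and the closing paragraphs of Section 21.0 agree. Section 9.7 randomises after consent and mails the manual to the intervention group with the accelerometer, before baseline is confirmed. Sections 18.1 and 21.0 also mention the mailed manual ahead of the baseline questionnaires. If knowing the arm shifts baseline answers by δ and leaves follow-up unchanged, the change contrast moves by the full δ, and a baseline-adjusted contrast by about ρδ.

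**The case against.** The strongest reply is that nothing here is wrong. The plan names its estimand, fits a standard model that estimates it, and says in Sections 10.1 and 10.2 that the pilot is not powered for these outcomes and that its effect sizes are tentative. That stands: a reader might infer that the planned analysis is biased or invalid, and the documents do not support this.

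Several further replies also stand:

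- **ρ is assumed.** Section 9.4 describes the optimism and gratitude scales as measuring dispositions. A high ρ is plausible there, and the gain would then sit at the lower end of the table.
- **The link to the next trial is not stated.** A reader might infer that the extra noise must enter the next sample size. Section 10.1 does not say that Cohen's d is derived from the mixed-model coefficients, or which SD is used. If d is computed from observed changes, altering the model alone would leave it unchanged. The sample size also has a second check.
- **GVHD.** A reader might take the missing stratum as a material defect. Its effect on actual precision is close to nil under the assumptions tried.
- **Social work.** Section 9.3 says only that these data will be considered. It does not put them in the Aim 2 effect model, and the pre-transplant evaluation it mentions precedes randomisation. A reader might infer a planned adjustment for a post-randomisation variable, but the plan merely leaves the possibility open.

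One reply does not stand: that the free group effect should be kept as protection in case participants know their arm before baseline. In that situation a change-from-baseline contrast is also distorted, and by more than a baseline-adjusted one.

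**Conclusion.** The point holds as an efficiency improvement. For any ρ below 1 the planned contrasts are less precise than a common-baseline analysis of the same data. The loss is moderate at ρ of 0.3 to 0.5 and small from 0.8 upward. These sizes rest on 35 and 30 per arm, a random-intercept covariance, missing at random and an assumed ρ. Under informative dropout neither model is protected, and the sensitivity analyses in Section 10.1 remain necessary.

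The primary feasibility and acceptability endpoint is untouched. Even with the gain, the intervals remain wide for planning purposes. The change is worth making because it uses data already in hand.

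**What to change.** 1. Fit the same mixed model with one baseline mean for both arms: drop the group main effect and keep the time-by-group terms for weeks 9 and 18. Alternatively, model weeks 9 and 18 only, with the baseline score as a covariate; estimating that slope costs roughly 2% of variance at this size.
2. State that the reported effect sizes are derived from this model, and which SD standardises them.
3. Include the GVHD randomisation stratum, with GVHD-by-time if wanted, noting that the further precision gain is small.
4. Reconcile Sections 5.1, 9.7, 18.1 and 21.0 so that baseline is complete before randomisation. Do not rely on the free group effect as a safeguard.
5. Keep social-work visits recorded after randomisation out of the main effect model, since treatment may influence them and adjustment could bias the effect in either direction. Report them by arm or in a labelled sensitivity analysis.

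The cost is analysis wording and a few degrees of freedom. Baseline scores and the GVHD stratum are already collected.
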